#### Statement of hypotheses:

\* Based on population history, it is postulated that the genomic architecture of individuals of African ancestry has been shaped by environmental pressures and natural selection in the context of high ambient temperatures in salt-poor conditions that may predispose to an increased sensitivity and avidity for sodium retention in African Americans.

- \* Increased dietary sodium intake is associated with vascular dysfunction and increased blood pressure in certain sub-sets of normotensive African Americans; and this effect is augmented in individuals with baseline evidence of vascular dysfunction.
- \* Increased dietary sodium intake is associated with changes in the whole blood epigenome as assessed by DNA methylation.
- \* Increased dietary sodium intake is associated with changes in the whole blood and urine transcriptome as assessed by RNA-seq.
- \* Increased dietary sodium intake is associated with changes in the skin, oral and gut microbiome.
- \* Increased dietary sodium intake is associated with whole blood epigenome/transcriptome molecular signature that predisposes to a chronic “pro-inflammatory state.”

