### **9.1 STATISTICAL HYPOTHESIS**

- 1) Increased dietary sodium intake will be associated with vascular dysfunction and increased blood pressure in the treatment group compared to the placebo group.
- 2) Increased dietary sodium intake will be associated with changes in the whole blood epigenome as assessed by DNA methylation in the treatment group compared to the placebo group.
- 3) Increased dietary sodium intake will be associated with changes in the whole blood and urine transcriptome as assessed by RNA-seq in the treatment group compared to the placebo group.
- 4) Increased dietary sodium intake will be associated with changes in the skin, oral and gut microbiome in the treatment group compared to the placebo group.
- 5) Increased dietary sodium intake will be associated with blood epigenome/transcriptome molecular signature in the treatment group compared to the placebo group.

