### **9.2 SAMPLE SIZE DETERMINATION**

Data will be tested for normality using the Shapiro-Wilk test. Continuous variables will be described as mean  $\pm$  standard deviation (SD) if normally distributed. Variables with skewed distribution (i.e. aldosterone, BNP, etc.) were logarithmically transformed prior to analyses and are presented as median and interquartile range (IQR). Categorical variables will be expressed as numbers (percentages).

When data are normally distributed, comparisons between the treatment (sodium intake) and control (placebo) groups will be made using paired Student's t-tests, and when data are non-

[figure not shown]
normally distributed, the Mann-Whitney U test will be employed. Chi-square test will be used for categorical variables. Tests for sodium intake effect on the primary outcomes without correction for period effect will be done using Mann-Whitney test on the differences. Tests for period effect will be assessed using two-sample Wilcoxon tests on the differences between treatment groups, and tests for carry-over effect will be assessed by a two-sample Mann-Whitney test on the averages in the two treatment periods. Correlations were determined with Pearson's correlation coefficient.

Additionally, we will evaluate the effects of sodium intake on changes in blood pressure, 24-hr ambulatory blood pressure monitoring (ABPM), biochemical markers, vascular functions, and specific transcriptome and epigenome by using a linear mixed model, with subject as a random effect, thereby accounting for the period, sequence, and carryover effects and to model the various sources of intra-individual and inter-individual variability. All statistical tests will be two-sided and P values  $<0.05$  will be regarded as significant. Statistical analyses will be carried out using SAS software (SAS Institute, Inc., Cary, NC, USA).

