**Sample size and statistical power:** We expect to enroll and randomize a total of 40 eligible subjects for this protocol. The sample size is assessed to detect meaningful effects of sodium intake on the study's primary outcomes and secondary outcomes, including changes in vascular function (PWV m/s), sitting SBP and DBP (mm Hg), ABPM (mm Hg), biochemical markers (plasma aldosterone, pg/mL, brain natriuretic peptide (pg/mL), as well as epigenome, transcriptome, and microbiome under an assumption about the effect size, standard deviation outcomes, correlation of measurements within individual. We estimated that a sample size of 28 participants will be required in a cross-over study to detect changes in PWV between high salt intake and control groups of 0.6 m/s (estimates based on [Pimenta et al.](#) ), with 80% power and  $P < 0.05$ , assuming common SD of 0.9 m/s for high sodium intake and control groups, and correlation of 0.3 within subjects (Figure 2). Accounting for a potential of 20% dropout during the study, the sample size would be 34.

In addition, the estimated sample size will provide us with more than 80 percent power to detect a difference of 6 mm Hg (SD=9 mm Hg) in sitting SBP between sodium intake and the placebo treatment at 0.05 significance level (estimates based on [Tzemos et al.](#) ). Similarly, the proposed sample size would give more than 90% power to detect significant changes in plasma aldosterone (pg/ml) and brain natriuretic peptide (pg/mL) between high sodium intake and control at 0.05 significance level . The sample size calculation was performed using a paired *t* test assuming no carryover effect and no interactions between subjects, treatments, and periods.

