#### 9.4.3 Analysis of the Secondary Endpoint(s)

The secondary endpoints will be assessed independent of the results associated with the primary endpoints; secondary endpoints include blood pressure, whole blood epigenome, and whole blood and urine transcriptome. The effect of treatment and placebo will be investigated will be investigated for each secondary endpoint, as detailed below.

The association between blood pressure (systolic and diastolic) and salt intake will be assessed using multiple linear regression with salt intake (two categories: treatment and placebo) as the exposure variable and blood pressure outcome variable. The effect size, p-value and 95% confidence interval of the regression model will be provided as results.

The effect of salt intake on gene expression will be investigated in a differential expression analysis to identify genes whose expression differs significantly between treatment and placebo. The gene expression data will be normalized, using the weighted trimmed mean of M-values (TMM) method, an optimal method for the normalization of mRNA count data. Genes with an expression less than 1 Count Per Million (CPM = count/sum [counts] x 1million) in at least 2 samples will be excluded because results from genes with extremely low expression are not reliable. Gene expression is generated as count data which follows a Poisson distribution; therefore, a negative binomial model will be fitted using the R library *edgeR* developed to handle the specificities of mRNA sequencing data. The model computes likelihood ratio tests for the coefficients whilst taking into account dispersion. A deviance of goodness of fit test will be carried out to identify genes where the model fit was poor indicating that the dispersion estimate is away from the average dispersion. Dispersion outliers will not be considered for the results because the deviance indicates low quality or marked expression difference for the gene. Finally, genes with a log fold change not equal to 0 and a false discovery rate adjusted p-value  $\leq 0.05$  will be reported as significantly differentially expressed between treatment and placebo. Multiple testing correction, for the total number of genes considered, will be carried out using the Benjamini-Hochberg method.

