The epigenetic effect of salt intake will be investigated through a two-sample t-test to identify methylation sites with significant methylation level difference between treatment and placebo. At a minimum of 5X coverage and an average coverage of 30X, the SureSelect-MethSeq (SS-Methseq) platform captures between 2.6 and 2.3 million methylation sites. After thorough processing and QC of the methylation data, using the Bismark pipeline, samples and methylation sites that passed all QC filters will be considered for the analysis. Each methylation site will be treated as a continuous variable and salt intake will be treated as a nominal variable with two categories (treatment and placebo), in the t-test. In such analysis, the methylation sites are assumed to be independent and there is, hence, a high burden of multiple testing due to the millions of sites being tested. Therefore, a significance threshold of p-value  $< 9 \times 10^{-8}$  will be applied to control for false positive findings; this threshold was derived from empirical work based on the Illumina EPIC array which has a lower density than the SS-Methseq platform but includes carefully selected sites that span the whole genome. The estimated mean difference, p-value and 95% confidence interval of the t-test will be presented as the results.

After the transcriptome, epigenome and microbiome data have been considered separately in the analyses described above and to understand the links between gene expression and methylation, an ensemble technique such as Random Forests will be used to leverage the high dimensionality of the data (number of features >> number of observations) and identify the best combination of predictors of salt intake in the transcriptome and epigenome data. Subsequently, the OTUs identified in the microbiome data will be integrated to find out if microbiome information improves the prediction accuracy of the omics data. This will provide further insights into the interplay between the three domains (microbiome, transcriptome and epigenome).

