#### **9.4.9 Exploratory Analyses**

Exploratory analyses will not be conducted.

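### The stated pro-inflammatory blood signature has no matching test: hypothesis 5 in 9.1 drops its content and direction, and no analysis supplies them

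*Combined protocol and SAP*

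**What the plan says.** The Statement of hypotheses in 4.1 lists as a separate item: "Increased dietary sodium intake is associated with whole blood epigenome/transcriptome molecular signature that predisposes to a chronic" pro-inflammatory state. Section 9.1 restates it as hypothesis 5: "Increased dietary sodium intake will be associated with blood epigenome/transcriptome molecular signature in the treatment group compared to the placebo group".

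The analyses that touch these data are:

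- **Expression (9.4.3):** edgeR models gene by gene, reporting "genes with a log fold change not equal to 0 and a false discovery rate adjusted p-value" of at most 0.05 (Benjamini-Hochberg).
- **Methylation (9.4.3):** a two-sample t-test at each site, "to identify methylation sites with significant methylation level difference between treatment and placebo", at p < 9×10^-8.
- **Combined (9.4.3):** an ensemble method such as Random Forests to "identify the best combination of predictors of salt intake in the transcriptome and epigenome data", to which microbiome features are later added.
- **Mixed model (9.2):** changes in "biochemical markers, vascular functions, and specific transcriptome and epigenome by using a linear mixed model". The genes and sites are not named. The sizing text lists "biochemical markers (plasma aldosterone, pg/mL, brain natriuretic peptide (pg/mL" and no inflammatory marker.

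Section 8.2.2 includes hs-CRP and a research tube for inflammatory markers such as IL-6 and TNF-alpha, and Table 2 in 1.3 has blood drawn at all four visits. Section 8.2 plans FACS profiling of immune cells at the same visits. Section 9 says that no formal SAP will be written, and 9.4.9 says "Exploratory analyses will not be conducted".

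**The concern.** The hypothesis in 4.1 has content (inflammation) and direction (towards it). Its statistical version has neither, and nothing downstream puts them back. Without a named set, score or direction, no result can be recognised in advance as supporting or refuting the claim. Inflammatory genes would have to be picked out once the results are known, and a reader could not tell a prediction from a selection.

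There is also a possible loss of power. If salt shifts many inflammatory genes slightly and together, a gene-wise screen corrected over the whole transcriptome suits that pattern poorly. The protocol provides no later place to repair this, since it foresees neither a SAP nor exploratory work.

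**Working it through.** **1. Content of each step**

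| Step | Features | Direction | Inflammatory content |
|---|---|---|---|
| 4.1 hypothesis | blood epigenome/transcriptome | pro-inflammatory | yes |
| 9.1 hypothesis 5 | blood epigenome/transcriptome | none | none |
| 9.4.3 expression | all genes kept | either; sign estimated | none |
| 9.4.3 methylation | all sites passing QC | either; sign estimated | none |
| 9.4.3 Random Forest | all features | not applicable | none |
| 9.2 mixed model | unnamed markers, genes and sites | not stated | none named |

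No row below the first can separate an inflammatory signature from any other.

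**2. The plan's own sample size**

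The 28 in 9.2 is for pulse wave velocity. SD of the within-person difference = 0.9 × √(2 × (1 − 0.3)) = 1.065 m/s. Standardised effect = 0.6 / 1.065 = 0.563. The normal approximation gives (1.960 + 0.842)² / 0.563² ≈ 24.7, so 25. The noncentral t gives 27, with power 82.0% at 28. The stated 28 therefore reproduces closely. The documents give no effect size or power for the signature, so step 3 rests on assumptions.

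**3. Gene-wise screen against a set score**

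Assumptions, none from the documents: 15,000 genes; a 200-gene inflammatory set that moves up together; inter-gene correlation ρ within the set of 0.05, 0.1 or 0.3; shift in SDs of the within-person salt-minus-placebo difference; paired tests throughout; Benjamini-Hochberg at 0.05; 300 simulated trials per setting. The sizes used are 28 (enrolment reported in the Addendum) and 40 (planned).

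The set score is the mean of the 200 differences, with SD = √((1 + 199ρ)/200). At ρ = 0.3 this is √(60.7/200) = 0.551, so a 0.2 SD shift has standardised effect 0.2/0.551 = 0.363 and power of about 45% at n=28. At ρ = 0.05 the SD is √(10.95/200) = 0.234, the effect is 0.855 and power is about 99%.

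| n | Shift (SD) | Any set gene passes the FDR | Set score detects the rise |
|---|---|---|---|
| 28 | 0.2 | 1–3% | 45–99% |
| 28 | 0.3 | about 8% | 80–100% |
| 28 | 0.5 | 49–74% | about 100% |
| 40 | 0.2 | 2–4% | 61–100% |
| 40 | 0.3 | 18–30% | 93–100% |
| 40 | 0.5 | 86–100% | about 100% |

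Ranges run over the three values of ρ. If a false positive outside the set also counts as a hit, a 0.3 SD rise at ρ = 0.1 gives 11–14% at n=28 and 27–28% at n=40 (150 trials per run). Hence the overall range of 1–14% for modest shifts at n=28.

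**4. A signature unrelated to inflammation**

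With the inflammatory set unchanged and 30 other genes shifted by 1.2 SD, at least one gene is significant in 100% of trials at both sizes, while an upward set test fires in about 1–3%. The shift was chosen to be large. It shows only that the wording of hypothesis 5 can be met without inflammation, not that this is likely.

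**The case against.** Several stronger readings are tempting, and the documents do not support them.

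- **That the Random Forest is the test of hypothesis 5, or that a fall in inflammatory genes would be counted as support.** The plan gives no decision rule for this hypothesis. It offers the Random Forest for understanding links between expression and methylation. Fold changes and mean differences carry a sign, so a fall would be visible as a fall.
- **That gene-by-gene prediction is all there is.** The mixed model in 9.2 also covers biochemical markers and some selected expression and methylation features, and its marker examples are not a closed list. It is too vague to test the hypothesis, but it exists.
- **That hypothesis 5 is positive whenever hypothesis 2 or 3 is.** Hypothesis 3 includes urine; hypothesis 5 is blood only.
- **That a broad inflammatory rise would be missed.** This depends on its size: at 0.5 SD it is often found gene by gene. The simulation covers neither the Random Forest nor the methylation tests, and its set score knows exactly which genes moved, which is its best case. On the other side, paired gene-wise tests flatter the plan, which specifies a two-sample test for methylation and states no pairing for edgeR.

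It is also fair to say that inflammation is not a listed objective or endpoint, that a predisposing signature need not be a uniform rise, and that 9.4.9 does not bar a prespecified secondary analysis. These points limit the weight of the concern. They do not supply the missing definition.

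**Conclusion.** The gap is real, and it rests on the text alone: the trial states a pro-inflammatory hypothesis and prespecifies nothing that could confirm or refute it. The size of the power loss is conditional. Under the assumptions in step 3, a coordinated rise of 0.2 to 0.3 SD is usually overlooked by the gene-wise screen at n=28 and detected far more often by a set score, while a 0.5 SD rise is often seen either way. Because this is a stated hypothesis and not a primary endpoint, the change is one that should be made, but it does not threaten the trial's main results.

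**What to change.** - **9.1, hypothesis 5:** restore the inflammatory content and the expected direction.
- **9.4.3:** add one inflammatory gene set, named before unblinding. Score it per person at the end of each period and compare salt with placebo within person, with period in the model, two-sided at 0.05 as in 9.2, and report the direction. This score covers expression only, so state that methylation is descriptive for this hypothesis unless a CpG set is named too.
- **9.2:** list IL-6, TNF-alpha and hs-CRP as supporting outcomes in the mixed model.
- **9.4.3:** state that the Random Forest is descriptive and is not evidence for hypothesis 5.

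If the investigators do not want to commit to a set, the alternative is to withdraw the pro-inflammatory claim from 4.1.

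The cost is some wording and one added analysis on samples already in the visit schedule. The downside is that the set must be chosen in advance, and a poorly chosen set would lose some of the power shown above.

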#### **9.4.4 Safety Analyses**

Not applicable.

#### **9.4.5 Baseline Descriptive Statistics**

Not applicable.

Baseline analysis stratified by treatment and placebo arms will be assessed based on clinical and demographic characteristics. Chi-square will be used to assess categorical variables and t-test will be used to assess continuous variables.

#### **9.4.6 Planned Interim Analyses**

Not applicable

#### **9.4.7 Sub-Group Analyses**

Primary and secondary endpoints will be compared based on age and sex differences stratified by treatment and placebo groups.).

#### **9.4.8 Tabulation of individual Participant Data**

Individual participant data will not be presented by time point.

#### **9.4.9 Exploratory Analyses**

Exploratory analyses will not be conducted.

### **10 REGULATORY AND OPERATIONAL CONSIDERATIONS**

#### **10.1 INFORMED CONSENT PROCESS**

##### **10.1.1 Consent/Accent Procedures and Documentation**

Consent will be obtained at the NIH Clinical Center during baseline visit. The GENE-FORECAST-SIT staff is experienced in administering consent and will escort potential participant to a private area of the Clinical Center to discuss the consent form.

The GENE-FORECAST-SIT staff will provide the individual a copy of the consent forms, read all sections of the consent form and solicit for any questions. The consent process will take between 20-30 minutes. The GENE-FORECAST-SIT staff is experienced in obtaining informed consent for NIH trials and will not coerce or influence potential participant to enroll in the trial. Potential participant will be given the opportunity to consult with others prior to providing consent. Consent for minors when they reach the age of majority  
Not applicable. Our study population will be 21-65 years of age.

**10.1.2 Considerations for Consent of NIH staff, or family members of study team members**  
Consent from staff members will be obtained by an individual independent of the staff member's team whenever possible. Otherwise, the consent procedure will be independently monitored by the CC Department of Bioethics Consultation Service in order to minimize the risk of undue pressure on the staff member.

**10.1.3 Participation of Subjects who are/become Decisionally Impaired**

Adults unable to provide consent are excluded from enrolling in the protocol. However, it is possible that subjects enrolled in the protocol may permanently lose the capacity to consent for themselves during the course of this study. In the event this occurs, the subjects will be withdrawn from the study. .

**10.2 STUDY DISCONTINUATION AND CLOSURE**

Study participant can discontinuation participation in protocol if any potential side effects occur due to consumption of study product (e.g., nausea, dizziness, rash). The possibility of a temporary suspension of the study is highly unlikely.

**10.3 CONFIDENTIALITY AND PRIVACY**

Participant confidentiality and privacy is strictly held in trust by the PI, participating investigators, and study staff. This confidentiality is extended to cover testing of biological samples and genetic tests in addition to the clinical information relating to participants. Therefore, the study protocol, documentation, data, and all other information generated will be held in strict confidence. No information concerning the study or the data will be released to any unauthorized third party without prior written approval of study participant.

All research activities will be conducted in as private a setting as possible.

Representatives of the NIH IRB and/or regulatory agencies may inspect all documents and records required to be maintained by the PI, including but not limited to, medical records (office, clinic) and pharmacy records for the participants in this study. The NIH Clinical Center will permit access to such records.

The study participant's contact information will be securely stored for internal use during the study. At the end of the study, all records will continue to be kept in a secure location for as long a period as dictated by the reviewing IRB.

Study participant research data, which is for purposes of statistical analysis and scientific reporting, will be transmitted to and stored on dedicated and secured NIH servers and the NIH electronic Clinical Trial Database (CTDB). This will not include the participant's contact or, identified by a unique study identification number.

The study data entry and study management systems used by the research staff will be secured and password protected. At the end of the study, all study databases will be identified and archived on PI's dedicated NIH server.

To further protect the privacy of study participants, a Certificate of Confidentiality has been issued by NIH. This certificate protects identifiable research information from forced disclosure. It allows the investigator and others who have access to research records to refuse to disclose

identifying information on research participation in any civil, criminal, administrative, legislative, or other proceedings, whether at the federal, state, or local level. By protecting researchers and institutions from being compelled to disclose information that would identify research participants. Certificates of Confidentiality help achieve the research objectives and promote participation in studies by helping assure confidentiality and privacy to participants.

